There is a growing body of evidence supporting the utility of rTMS in a variety of neuro-psychiatric conditions in adults and children (1, 2). Although these disorders encompass a diverse list, regardless of the underlying etiologies, the neurophysiological alteration manifests itself through under or over activation of the cerebral cortex. rTMS is a noninvasive method which induces a magnetic field in the targeted area of the cerebral cortex and hence, alters the excitability of the neurons. While low-frequency magnetic stimulation (<1 Hz) is known to suppress the cortical activity, high-frequency stimulation (5-20 Hz) enhances the cortical activity (3). Depending on the type and nature of the underlying disorder, high or low frequency stimulation may be applied to mitigate the abnormal cortical activity and therefore modulate the cortical excitability. The safety of rTMS has been the subject of a review article by Krishnan et al, who have cited 35 manuscripts pertaining to the use of rTMS in various neuro-psychiatric conditions (4).

Use of rTMS in ASD has been the subject of several extensive reviews (5, 6, 7). Aside from a few exceptions, these studies were open label and included a small number of subjects. In the majority of the studies, the rTMS parameters were quite conservative, delivering between 50-200 pulses per session and yielding mixed results in behavioral rating scales or neuropsychological measures. In most cases, the bilateral dorsolateral prefrontal cortex was targeted. Low-frequency stimulation in this area has correlated with improvement in repetitive behavior. High-frequency rTMS stimulation on the premotor cortex has resulted in an improvement in motor coordination in ASD. High-frequency rTMS to the bilateral medial prefrontal cortex in adults with ASD yielded improvement in social relatedness.

The mirror neurons, concentrated in the inferior frontal and parietal lobes in humans, play a substantial role in imitating activities (8). This function is quintessential in acquiring language, nonverbal communication, empathy, social behavior and reciprocal interactions (9, 10, 11). The above attributes constitute the core deficits in children with ASD (12, 13). rTMS stimulation of the mirror neurons has not been attempted in the past.

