1. Children with ASD exhibiting significant anxiety or contact avoidance, precluding them from cooperating with the procedure
2. Children with a known diagnosis of seizures

INTERVENTION:

The rTMS treatment sessions will be scheduled 2 days a week for 5 weeks. In the beginning of each session, a single pulse stimulation will be utilized to determine the motor threshold. This is accomplished by increasing the intensity of the stimulation to achieve a twitch in the thenar muscle on the right hand. Eighty percent of the motor threshold will be applied for the treatment session. Each treatment session will consist of 10 minutes of HF rTMS delivery to the IPL, either the right or the left side, according to the paradigm detailed in the table below.

Frequency	10 Hz
Burst duration	10 seconds
Inter-burst intervals	20 seconds
Session time	10 minutes
Total stimulations per session	2000
Intensity	80% of motor threshold

The rTMS paradigm

rTMS TARGETING OF THE IPL:

For targeting the IPL, we are planning to use the standard 10/20 electrode placement system used for EEG recording. The IPL localizes to the Brodmann areas 7 and 40 and the P3/4 electrodes (15). A recent publication by Huang et al used sophisticated analysis of functional MRI and resting state functional connectivity in ASD and proposed multiple potential targets for neurostimulation including DLPFC, angular

gyrus and inferior frontal gyrus. Angular gyrus falls under Brodmann 40 and P3/4 EEG electric placement and overlaps with our proposed targeting of the IPL (16).

TREATMENT GROUPS AND THE EXPERIMENTAL DESIGN:

The patients will be randomized at the time of recruitment to either receiving left or right IPL stimulation. A standard shamming technique will be utilized to blind the patient regarding the treatment targeting (17). The neuropsychologist obtaining and interpreting the outcome measures will also be blinded. Only the clinician delivering the rTMS treatment will have a knowledge about the treatment targeting.

OUTCOME MEASURES:

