We aim to recruit the subjects over a 2-year period. Each subject will receive the rTMS treatments 2 days a week for a period of 5 weeks and will be followed for three months after the intervention.

GENDER OF SUBJECTS:

There will be no gender preference when enrolling for this study.

AGE OF SUBJECTS:

We aim to recruit children and young adults with ASD. The subjects will be children 8 years or older and young adults up to 25 years old.

RACE & ETHNIC ORIGIN:

There will be no restrictions in enrollment based upon race or ethnic origin.

DATA ANALYSIS:

The numerical values generated by the above semi-quantitative measures (SRS, RRBs, NIHTB, DKEFS, WRAML-3) before and after treatment and after 3-moth follow up will be entered into an excel database and used for statistical analysis. For establishing statistical significance between the mean values before and after treatment, student t-test and confidence intervals will be used.

RISKS:

rTMS is a noninvasive method and not associated with any risks.

ADVERSE EVENTS:

The adverse effects of rTMS are mild and benign and consistent of transient headaches or scalp discomfort. Occurrence of seizures is quite rare; Krishnan et al. reported a total of 2 cases of seizures in 332 subjects participating in 35 trials of rTMS between 2004 and 2014. Both patients did have clear risk factors for seizures. These seizures occurred with the high-frequency stimulation of 15-20 Hz and short inter burst intervals which will be avoided in our protocol. Our study protocol will exclude all patients with history of epilepsy. Medications which may lower the seizure threshold will be avoided altogether if possible.

SEIZURE PROTOCOL:

If the patient should experience a seizure during the treatment, the following protocol will be followed

1. Universal seizure precautions and safety
2. Monitoring the vital signs

3. Calling the code and transferring the patient to the emergency room. If the seizure lasts for less than a minute, no specific treatments or interventions are necessary. However, the patient will be withdrawn from the study protocol. If the seizures are prolonged, in the emergency room, further decisions will be made regarding performing an EEG or other necessary treatments.

POTENTIAL BENEFITS TO THE SUBJECT AND SOCIETY:

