Currently, there are no treatment options to mitigate The cognitive function and in particular, social cognition in patients with ASD. Based on the current research, the patients may directly benefit from the effects of rTMS on cortical modulation. If this study yields beneficial results, we will proceed with another NIH grant to fund this study on a larger scale.

METHOD OF SUBJECT IDENTIFICATION AND RECRUITMENT:

Patients who are referred to our clinic for evaluation of their developmental disabilities and confirmed to have ASD will be approached to participate in the study.

PROCESS OF CONSENT:

The informed consent will be obtained by the PI or the Co-PI's. The study setup, purpose, risks and benefits will be discussed at length with the patients/family. They will be given the opportunity to weigh their decision prior to giving/refusing consent. If consent is declined, no further effort will be made in persuading them otherwise.

Determination of Mental Competence for Consenting:

Subjects' mental competence for consenting will be determined based on the developmental milestones, in particular language development and intelligence as determined by the neurological evaluation as well as the neuropsychological assessment. The patients would be categorized into the following groups:

For all minors, 13 years and younger, parental consent will be obtained.

For teenagers ages 13-18 in addition to parental consent, an assent will be obtained.

For individuals between 18-25 years of age with mild, moderate or severe mental retardation as determined by the neuropsychological evaluation, parental consent will be necessary. If the degree of intellectual impairment is mild, an assent will also be obtained. For individuals older than 18 who are mentally handicapped, the parents need to present POA documentation in order to sign the consent form.

DOCUMENTATION OF CONSENT:

The consent will be documented in writing and the signed consent form will be kept in the patient's medical record along with a copy that will be placed in the secure research file accessible to study personnel only. The patient/family will receive a copy of the signed consent form.

COSTS AND PAYMENT:

The subject will not incur any additional costs other than those accrued from their standard evaluation and treatment. The patients will receive a stipend for participating in this research (\$ To be determined)

DATA STORAGE AND CONFIDENTIALITY:

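### The protocol plans no collection or summary of adverse events or session completion, so the pilot has no planned safety or tolerability result; a short checklist and one table would supply it

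*Combined protocol and SAP*

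**What the plan says.** All three aims concern efficacy. INTERVENTION describes finding the motor threshold and delivering the pulses; it does not ask about symptoms or record whether the session was completed. OUTCOME MEASURES lists neuropsychological and parent-rated instruments, given at baseline, after the treatment course and three months later. DATA ANALYSIS takes as its data "The numerical values generated by the above semi-quantitative measures (SRS, RRBs, NIHTB, DKEFS, WRAML-3" and compares means by t-test and confidence intervals.

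Safety appears in three short sections:
- RISKS says that the method carries none.
- ADVERSE EVENTS, directly after it, says "The adverse effects of rTMS are mild and benign and consistent of transient headaches or scalp discomfort" and adds that seizures are rare, citing a review with two among 332 participants.
- SEIZURE PROTOCOL covers vital signs, transfer and withdrawal of the patient.

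SUBJECT WITHDRAWAL allows a participant to leave at any time and does not ask for the reason to be recorded.

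On exposure, BACKGROUND describes most earlier studies in autism as "delivering between 50-200 pulses per session"; the paradigm table gives "Total stimulations per session 2000". On purpose, the protocol says: "If this study yields beneficial results, we will proceed with another NIH grant to fund this study on a larger scale".

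**The concern.** Expected effects are named, but no step makes anyone ask about them. A missing analysis method can be written before the data are examined. A transient headache that nobody asked about at a session cannot be recovered, and some participants with communication difficulties may not volunteer it.

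Tolerability and session completion are among the things that 20-30 subjects can usefully describe, and the planners of a larger study would need them. The earlier autism studies, as BACKGROUND describes them, mostly used far fewer pulses per session, and it says that mirror-neuron stimulation had not been tried before. They are therefore a weak substitute for the trial's own data. Followed as written, the trial could not report event rates overall or by side, or how many of the planned sessions were delivered.

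**Working it through.** **1. The plan's own pulse count.** Inputs from the paradigm table: "Frequency 10 Hz", "Burst duration 10 seconds", "Inter-burst intervals 20 seconds", and a session of 10 minutes (600 s).
- Bursts per session = 600 / (10 + 20) = 20.
- Pulses per burst = 10 s x 10 Hz = 100.
- Pulses per session = 20 x 100 = 2000, which matches the table exactly.
- If the interval ran from onset to onset, the count would be 600/20 x 100 = 3000, which does not match. The 20 seconds are therefore off-time.

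**2. Comparison with BACKGROUND.** 2000/200 = 10 and 2000/50 = 40. The ratio is 10 to 40 per session, against the majority of earlier autism studies as the protocol describes them.

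**3. Opportunities to ask.** Twice weekly for five weeks is 10 sessions per subject; with 20-30 subjects, 200-300 sessions.

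**4. Precision if events were collected.** With 0 events in n subjects, the exact two-sided 95% upper limit is 1 - 0.025^(1/n). The protocol does not state the allocation ratio; the per-arm rows assume equal allocation.

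| Group | n | Upper limit with 0 events |
|---|---|---|
| Overall | 20 | 16.8% |
| Overall | 30 | 11.6% |
| One arm | 10 | 30.8% |
| One arm | 15 | 21.8% |

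If 10% of subjects report an event (an assumed rate), the exact interval is 1.2% to 31.7% for 2/20 and 2.1% to 26.5% for 3/30.

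**5. Chance of seeing at least one event**, 1 - (1 - p)^n:
- Common event, p = 10% (assumed): 1 - 0.9^20 = 88%; 1 - 0.9^30 = 96%.
- Seizure at the cited rate, p = 2/332 = 0.60% (exact 95% interval 0.07% to 2.16%): 11% with 20 subjects, 17% with 30.

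Collection would therefore be informative about common events and nearly uninformative about seizures. Even the smallest overall upper limit with no events, 11.6%, is far above 0.60%.

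**The case against.** Three stronger readings are tempting, and the documents support none of them.

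- **That the trial would yield no safety information at all.** A seizure during treatment would be noticed and acted on under SEIZURE PROTOCOL. DATA STORAGE AND CONFIDENTIALITY puts all health information obtained into the database. The repetitive-behaviour scale has a self-injury subscale, and SRS-2 scores can worsen, so behavioural deterioration is partly in the analysed data. What stands is narrower: storing what is obtained does not require anyone to obtain it, and no safety result is planned.
- **That the pulse ratio shows greater danger.** The documents do not link pulse count to adverse events. They attribute the two cited seizures to patients with risk factors and to stimulation at 15-20 Hz with short intervals, which the protocol says it avoids; it uses 10 Hz at 80% of motor threshold. The ratio is not a comparison with rTMS in other conditions either. It shows only that the earlier autism studies cannot stand in for this trial's own tolerability data.
- **That no recording form exists.** Case report forms are not among the documents. One can say only that the protocol describes no collection step.

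It is also fair to object that the trial states no safety aim, that rates by side will be very imprecise, and that asking about scalp discomfort could reveal the stimulated side to the blinded neuropsychologist. The first does not make tolerability less useful to a pilot. The other two limit how the data should be collected and labelled, and the fix allows for them.

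**Conclusion.** The point holds as a cheap improvement that should be made. The aims, session procedure, outcome battery and analysis section plan no elicitation, recording or summary of adverse events or session completion, in a trial of children and young adults at 2000 pulses per session against the 50-200 cited. Checklist items not asked at a session cannot be recovered for that session, although a checklist added during the two-year recruitment would still cover later ones.

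The gain is limited. The table would describe common tolerability events. It could not rule out a seizure rate above 2/332 or compare the two sides with any useful precision. The per-arm limits assume equal allocation, and the 10% event rate is an illustration; neither is in the documents.

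Separately, RISKS and ADVERSE EVENTS contradict each other, one denying any risk and the other listing headache, scalp discomfort and rare seizures. The two sections must be reconciled.

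**What to change.** - Add a short fixed checklist: headache, scalp discomfort, seizure, other; severity; duration; session completed or not; reason for any withdrawal.
- At each of the 10 sessions, have it completed by the treating clinician, who already knows the side.
- At the assessments after treatment and at three months, have it completed by named existing study staff other than the blinded neuropsychologist, and withhold the answers from that assessor.
- Add to DATA ANALYSIS the subject-level counts and rates of each event and the sessions completed, overall and by side, with exact two-sided 95% confidence intervals for the rates, labelled descriptive.
- Reconcile RISKS with ADVERSE EVENTS.

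Cost: a minute or two per session, a similar brief contact at the two later assessments, and one extra table. No dose, schedule or clinical rule changes.
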